7.2 SYMPTOMS ASSESSMENT

The symptoms will be assessed throughout 24 months (approximately every 3 months) for all patients with confirmed diagnosis of MC (any type). The symptoms include:

- Stool frequency (number of stools per day).
- Stool consistency (type of stool according to the Bristol Stool Chart – Figure 1)
- Nightly diarrhea
- Urgency (0 = no urgency, 1 = need to defecate within 30 minutes, 2 = immediate need to empty the bowel, 3 = fecal incontinence - have to go immediately to the toilette),
- Difficulties staying continent with a respective bowel movement (yes/no)
- Abdominal pain (0 = no pain, 1 = mild, 2 = moderate, 3 = severe pain)

The Bristol Stool Chart is used to monitor change in intestinal function and is widely used both in clinical practice and research. This scale classifies the form of human faeces into seven categories (figure 2).

[figure not shown]

Figure 2 – Bristol Stool Chart

During the first appointment of the study, the symptoms will be captured by the physician into the eCRF by interviewing all the eligible patients who will report to the previous 7 days. During the subsequent appointments the symptoms will **only** be recorded by the MC patients, using the patient diary. The patient diary should be completed on a daily basis for the period of 7 days before the next appointment to the specialist. The symptoms to be captured in the diary include the total number of stools and its type (according to Bristol Stool Chart) and therapies used (pharmacological/non-pharmacological) between appointments. The physician should clarify with the patient any inconsistency or missing information found in the patient diary.

The patient will be given at each appointment the necessary number of diaries to cover the period until the next scheduled appointment.

In case the patient forgets or loses the diary at one appointment, the investigator and the patient will have to estimate the number of stools and watery stools and this situation should be recorded in the eCRF (as estimated result) due to missing diary.

At each appointment, the investigator calculates the mean number of stools and of watery stools per day according to the formula:

The number of stools (any type) and watery stools in the week prior to the appointment will be divided by number of days with entries.

The number of stools and the type will not be evaluable if less than 5 days of entries are found and there is no possibility to collect any further information regarding that week. The day corresponding to the preparation of endoscopy will not be used to assess these symptoms.

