 - number of stools per day (the mean number of stools and watery stools per day will be calculated by summing the number of stools [any type] and watery stool that occurred over the week before the time point of assessment divided by 7 days).
 - type of stool (1 to 7 - Bristol Stool Chart)
 - nightly diarrhea
 - urgency (0 = no urgency, 1 = need to defecate within 30 minutes, 2=immediate need to empty the bowel, 3 = fecal incontinence - have to go immediately to the toilette)

- difficulties staying continent with a respective bowel movement
- abdominal pain (0 = no pain, 1 = mild, 2 = moderate, 3 = severe pain)
- Laboratory parameters – hemoglobin, platelets, leukocytes, neutrophils, eosinophiles, basophiles, monocytes, lymphocytes, erythrocyte sedimentation rate (ESR), C-reactive protein (CRP), iron and transferrin.
- Concomitant medications
- Changes in concomitant illness (worsening of previous conditions, new condition)

At diagnosis of MC and every 3 months up to month 24:

- Fecal sample – for assessment of calprotectin, ECP and EPX levels.

In addition, at Month 24 only:

- Date of colonoscopy with sampling of colonic specimens
- Result of colonoscopy: normal/abnormal - describe
- Date and result of histological assessment :
 - Geboes Index (grade for each of the colon segments: rectum, sigmoid, descending, transverse and ascending) – see Section 7.4.2.
 - IEL in the surface epithelium (not observed, < 5 IEL/100 surface epithelial cells, > 5 and < 20 IEL/100 surface epithelial cells, ≥20 IEL/100);
 - Thickness of the subepithelial collagen layer (not observed, <5 µm; > 5 and < 10 µm; ≥ 10 µm).

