8.3 DEFINITIONS OF INTEREST

8.3.1 Clinical outcomes (applicable to all MC subtypes – CC, LC and IC)

- **Clinical activity:** mean of ≥ 3 stools per day or mean of ≥ 1 watery stool per day.³⁸
- **Clinical remission:** mean of < 3 stools per day and mean of < 1 watery stool per day.³⁸

The mean number of stools and watery stools per day will be calculated by summing the number of stools (any type) and watery stool that occurred over the week before the time point of assessment divided by 7 days.³⁸

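### Section 7.2 drops only the preparation day and leaves the order of the month 24 colonoscopy and appointment open, so other procedure-affected days can enter the stool mean

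*Protocol*

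**What the plan says.** - **Diary window.** Protocol 7.2: "The patient diary should be completed on a daily basis for the period of 7 days before the next appointment to the specialist". The window is tied to the appointment, not to the colonoscopy.
- **Exclusion.** Protocol 7.2: "The day corresponding to the preparation of endoscopy will not be used to assess these symptoms". The colonoscopy day and the days after it are not mentioned.
- **Minimum data.** Protocol 7.2: stool number and type "will not be evaluable if less than 5 days of entries are found" and no further information on that week can be obtained.
- **Divisor.** In 7.2 the weekly count "will be divided by number of days with entries". In 8.3.1 it is the count that "occurred over the week before the time point of assessment divided by 7 days"; 7.1 has the same fixed 7, both at baseline and at follow-up.
- **Classification.** Protocol 8.3.1: remission is a "mean of < 3 stools per day and mean of < 1 watery stool per day"; activity is a "mean of ≥ 3 stools per day or mean of ≥ 1 watery stool per day".
- **Month 24.** Section 7.1 adds a colonoscopy with biopsies at this follow-up visit only and records the "Date of colonoscopy with sampling of colonic specimens". The appendix schedule puts colonoscopy, histology, symptoms and fecal sample in the same month 24 column. Neither place gives the order of colonoscopy and appointment.

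**The concern.** The exclusion in 7.2 recognises that the procedure disturbs the stool count but covers one day only. If the colonoscopy precedes the appointment by a few days, the stool mean includes the procedure day and days after bowel cleansing. Nothing flags this, because the week still has enough entries to be scored.

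Month 24 is the only follow-up visit with histology. Its clinical classification feeds three secondary analyses in 8.2 and 9.1: the month 24 remission proportion, the AUC of the fecal markers against clinical activity at that visit, and the estimating-equation model relating clinical to histological features. That model has paired data at only two time points, baseline and month 24.

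**Working it through.** **1. The plan's own figure.** Section 9.2 expects 300 × 0.10 = 30 patients with MC. One misclassified patient therefore moves the month 24 remission proportion by 1/30 = 3.3 points, if all 30 are evaluable.

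**2. Which days enter.** Call the appointment day 0 and the diary days −7 to −1. Let the colonoscopy be *d* days before the appointment, and assume that preparation is the day before it (the protocol does not say).

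- *d* = 0: preparation is day −1 and is dropped. No procedure or later day is in the window.
- *d* = 1: preparation is dropped; the colonoscopy day is counted.
- *d* = 2 to 6: preparation is dropped; the colonoscopy day and *d* − 1 later days are counted.
- *d* = 7: preparation falls outside the window, nothing is dropped, and the colonoscopy day is counted.
- Colonoscopy after the appointment: no effect.

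The exclusion operates for *d* = 0 to 6. In 6 of these 7 placements the colonoscopy day is counted, and in 5 at least one later day is too. These are counts of possible placements, not probabilities. Six entries remain, which is above the minimum of 5.

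**3. Effect on the classification.** Let *k* of the 6 counted days have a fraction *f* of usual output. Both *k* and *f* are assumptions. Recorded mean = true mean × (6 − *k* + *fk*)/D, where D is 6 (days with entries) or 7 (fixed). The true mean at which the recorded mean reaches the cut-off is 3 (stools) or 1 (watery) divided by that factor.

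| *k* | *f* | Factor, D = 6 | Stools | Watery | Factor, D = 7 | Stools | Watery |
|---|---|---|---|---|---|---|---|
| 0 | – | 1.000 | 3.00 | 1.00 | 0.857 | 3.50 | 1.17 |
| 1 | 0 | 0.833 | 3.60 | 1.20 | 0.714 | 4.20 | 1.40 |
| 2 | 0 | 0.667 | 4.50 | 1.50 | 0.571 | 5.25 | 1.75 |
| 1 | 0.5 | 0.917 | 3.27 | 1.09 | 0.786 | 3.82 | 1.27 |
| 2 | 0.5 | 0.833 | 3.60 | 1.20 | 0.714 | 4.20 | 1.40 |

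An active patient is scored as in remission only if **both** true means lie below the limits in the row.

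**4. The opposite direction.** Take a remission patient with 2 stools and 0.5 watery stools per day, so 3 watery stools over 6 days. Suppose residual preparation adds watery stools on the colonoscopy day (also an assumption). Three extra give (3 + 3)/6 = 1.0 and the patient is scored active. With D = 7, four extra are needed: (3 + 4)/7 = 1.0.

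**5. The divisor alone.** The *k* = 0 row needs no assumption about output. Once the preparation day is dropped, dividing six days' stools by 7 multiplies the mean by 6/7 = 0.857, a 14% understatement. This applies even when the colonoscopy is on the appointment day.

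**6. Would dropping more days work?** Dropping preparation and colonoscopy leaves 7 − 2 = 5 entries, just enough. One further day leaves 4, and the week is no longer evaluable from the diary.

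**The case against.** A reader might infer that the protocol always averages in post-procedure days, or that it systematically turns active disease into remission at month 24. The documents support neither.

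- **Timing.** The appendix lists colonoscopy and symptoms under the same visit. If they share a day and preparation is the day before, the one-day exclusion is sufficient. That the rule exists shows only that preparation was expected inside the diary week, which fits a same-day colonoscopy equally well. This stands: the effect is conditional on a timing that the protocol leaves open.
- **Output after cleansing.** The protocol gives no figure. Zero output is the extreme case, and at half output the limits move much less. This stands.
- **Direction.** Residual preparation may raise the watery count on the colonoscopy day, so a bias in one direction cannot be claimed. This stands.
- **Two criteria.** Patients enter with watery diarrhea, and any whose true watery mean stays above the limit remain active whatever the total count. No share of misclassified patients can be derived, because the protocol gives no distribution of stool means.
- **Importance.** The analyses affected are secondary, descriptive or exploratory, at one of eight follow-up visits, with no predefined hypothesis. This limits the weight of the point.

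None of this removes the defect. For a colonoscopy 1 to 6 days before the appointment, the rule as written scores affected days as ordinary ones.

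**Conclusion.** The concern holds in conditional form. The protocol fixes neither the order of the month 24 colonoscopy and appointment nor the handling of any procedure-affected day other than preparation. With a colonoscopy 1 to 6 days before the appointment (preparation assumed the day before), clinical activity at month 24 can be misclassified. With one on the appointment day or later, no post-procedure day enters.

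Under D = 6, one or two affected days shift the effective cut-offs from 3 stools to between 3.27 and 4.50, and from 1 watery stool to between 1.09 and 1.50. The range runs from half output on one day to zero output on two. Errors towards active disease are also possible, so the net direction is unknown. The primary endpoint, MC prevalence, is not affected.

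The contradiction over the divisor is firmer, since it rests on the text alone.

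**What to change.** 1. In 7.2, for month 24 only, define the diary week as the 7 days before the appointment or the 7 days before bowel preparation starts, whichever ends earlier, and state that no day from the start of preparation onward is used. This keeps 7 possible entries, does not push the week past the visit at which the diary is returned, and leaves the scheduling of the colonoscopy alone. Baseline needs no such rule, because symptoms there are taken by interview at the first appointment.
2. Choose one divisor and use it in 7.1, 7.2 and 8.3.1. Dividing by the number of days with entries agrees with the 5-day minimum and with any excluded day. A fixed 7 understates the mean whenever fewer than 7 days are counted.

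The cost is a sentence in 7.2, aligned wording in 7.1 and 8.3.1, and an instruction with the diary dispensed at month 21. The small downside is that the month 24 diary week may end a few days before the appointment.

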7.3 ENDOSCOPIC ASSESSMENT

All eligible patients will undergo a complete colonoscopy as part of the routine procedures for differential diagnosis. The findings of the colonoscopy will be collected into the eCRF.

During the complete colonoscopy biopsies will be taken from the colonic segments for histological examination – see section 7.4.

7.4 HISTOLOGICAL ASSESSMENT

7.4.1 Sampling and shipment procedures

The sampling of specimens for screening of MC is as follows:

- Four biopsies will be collected from each colon segment: rectum, sigmoid, descending, transverse and ascending.
- The biopsies will be fixed in buffered formalin 4% and will be sent to central lab (pathologist) through courier at room temperature along with a study specific form. All materials and courier arrangements will be provided by the Central Lab.

The central pathologist will confirm the diagnosis of microscopic colitis.

Contact of central pathologist:
[name]
Serviço de Anatomia Patológica
Hospital de São João
[name]
[name].

7.4.2 Histological criteria for diagnosis of MC and subtypes

The diagnosis of MC and subtypes (confirmed/not confirmed) can only be established if the histological findings are present in at least one biopsy of at least two segments of the colon. For each segment the worst values of both biopsies are to be used for evaluation. The values used for evaluation have to be marked.

The histopathological criteria used for confirmation of Microscopic colitis (MC) regardless of the subtype are:

- a) Abnormal intraepithelial lymphocytes (IEL) > 5 IEL per 100 surface epithelial cells of the colonic mucosal membrane, **and/or**
- b) A subepithelial collagen layer > μ 5 m

Colonic biopsies are considered normal when the number of surface epithelial cells is \leq 5 IEL/100 surface epithelial cells, the collagen band is \leq 5 μ m and Geboes grade < 3.1.

The histopathological criteria used for confirmation of Lymphocytic colitis (LC) are:

- a) Abnormal intraepithelial lymphocytes (IEL) \geq 20 IEL per 100 surface epithelial cells of the colonic mucosal membrane
- b) A subepithelial collagen layer < 10 μ m

The histopathological criteria used for confirmation of Collagenous colitis (CC) are:

- a) An irregularly thickened subepithelial collagen layer \geq 10 μ m

The histopathological criteria used for confirmation of Incomplete colitis (IC) are:

- a) Thickened subepithelial collagen layer (> 5 μ m and < 10 μ m) **and/or**

- b) Abnormal IEL (> 5 and < 20 lymphocytes per 100 surface epithelial cells of the colonic mucosal membrane).

Geboes index, is a validated score for evaluating histologic disease activity and is presented in Table 1. Active histologic disease can be defined as a Geboes grade ≥ 3.1 (presence of epithelial neutrophils with or without crypt destruction or erosions).

Table 1 - Geboes score for assessment of histologic disease activity for each segment of the colon

Structural (architectural changes)	Grade 0	Colonic segments				
		R	S	D	T	A
	Subgrades					
No abnormality	0.0					
Mild abnormality	0.1					
Mild or moderate diffuse or multifocal abnormalities	0.2					
Severe diffuse or multifocal abnormalities	0.3					
Chronic inflammatory infiltrate	Grade 1					
	Subgrades					
No increase	1.0					
Mild but unequivocal increase	1.1					
Moderate increase	1.2					
Marked increase	1.3					
Lamina propria neutrophils and eosinophils	Grade 2					
	2A Eosinophils					
No increase	2A.0					
Mild but unequivocal increase	2A.1					
Moderate increase	2A.2					
Marked increase	2A.3					
	2B Neutrophils					
No increase	2B.0					
Mild but unequivocal increase	2B.1					
Moderate increase	2B.2					
Marked increase	2B.3					
Neutrophils in epithelium	Grade 3					
	Subgrades					
None	3.0					
< 5 % Crypts involved	3.1					
< 50 % Crypts involved	3.2					
> 50 % Crypts involved	3.3					
Crypt destruction	Grade 4					
	Subgrades					
None	4.0					
Probable - local excess of neutrophils in part of crypt	4.1					
Probable - marked attenuation	4.2					
Unequivocal crypt destruction	4.3					
Erosion or ulceration	Grade 5					
	Subgrades					
No erosion, ulceration, or granulation tissue	5.0					
Recovering epithelium + adjacent inflammation	5.1					
Probable erosion focally stripped	5.2					
Unequivocal erosion	5.3					
Ulcer or granulation tissue	5.4					

R - rectum; S - sigmoid; D - descending; T - transverse; A - ascending

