Abnormal chronic inflammation in the lamina propria is a typical histological characteristic but does not allow a distinction between the subtypes of MC.¹⁵ CC is characterized by a thickened subepithelial collagen layer, i.e., $> 10 \mu\text{m}$ in well-oriented biopsies cut perpendicularly to the surface,¹⁶ and lymphocytic colitis (LC) is characterized by an increased number of intraepithelial lymphocytes (IEL), i.e., ≥ 20 IEL per 100 epithelial cells. Colonic biopsies are considered normal in the absence of chronic inflammation in the lamina propria, when the number of surface epithelial cells is ≤ 5 IEL/100, and the collagen band is ≤ 5 micrometers.^{10,17}

Recent studies have shown that histological features in the individual patient are inconsistent over time, as findings of MC interchange with chronic (non-specific) inflammation or incomplete signs of MC at prior or repeat colonoscopy, and the overlap between CC and LC is significant.^{8,18,19} This histological interchange between MC subtypes and the incomplete identification of some patients have led to the introduction of a third subtype designated as incomplete MC (IC). The histological criteria for IC are an abnormally thickened collagenous band (> 5 and $< 10 \mu\text{m}$), and /or an increased number of intraepithelial lymphocytes (> 5 and < 20 per 100 epithelial cells) without reaching the thickness or number required for the diagnosis of CC or LC.¹

Epidemiologic studies show that MC is almost as common as classic IBD (i.e. Crohn's disease and ulcerative colitis).^{13,20-22} The incidence of MC appears to be rising and in some countries it may be diagnosed in 10% of patients investigated for chronic non-bloody diarrhoea, and in 20% or more of such patients older than 70 years.^{13,20} After a period of rising incidence figures, the data have been more divergent in recent studies. Incidence rates of 2.6/100,000 to 10.8/100,000 inhabitants have been reported for CC, and an annual incidence rate of 2.2 to 14 per 100,000 inhabitants for LC.^{13,20-22} Patients with MC are predominantly elderly women, and the average age at diagnosis is approximately 65 years, but a recent study shows that the age at diagnosis is increasing and a large proportion are now diagnosed in their seventies. This may be attributable to the rising of life expectancy observed over the last decades.²³ The female predominance is very clear in MC, but is less pronounced for LC than for CC.²¹

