8 ENDPOINTS

8.1 PRIMARY ENDPOINT

Number of patients with confirmed diagnosis of MC (any subtype) over the total number of colonoscopies performed in all patients included in the study.

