8.2 SECONDARY ENDPOINTS

- Proportion of patients with confirmed diagnosis of each subtype of MC (CC, LC and IC)
- Age, gender, BMI, smoking status, duration of symptoms, stool frequency and consistency (type), familial history of IBDs, comorbidities, previous pharmacological/ non-pharmacological therapies and laboratory parameters to be compared between MC patients and non-MC patients.
- Treatments (pharmacological/non-pharmacological) prescribed by specialist for patients with MC diagnosis
- Number of stools and type (Bristol stool form scale), urgency and abdominal pain over the last 7 days before each time point of assessment for patients with MC diagnosis.
- Proportion of MC patients with clinical remission at each data collection time point (month 3, 6, 9, 12, 15, 18, 21 and 24)
Clinical remission: mean of < 3 stools per day and mean of < 1 watery stool per day
- Proportion of MC patients with histological remission at month 24.
See section 8.3.2 for definition of histological remission
- Age, gender, BMI, smoking status, duration of symptoms, stool frequency and consistency, familial history of IBDs, age at diagnosis of MC, time to diagnosis of MC, comorbidities, pharmacological/non-pharmacological therapies, laboratory parameters and histological features, compared with clinical activity status (active/non active) described for patients with MC diagnosis.
- Age, gender, BMI, smoking status, duration of symptoms, stool frequency and consistency, familial history of IBDs, age at diagnosis of MC, time to diagnosis of MC, comorbidities, pharmacological/non-pharmacological therapies, laboratory parameters, compared with histological features, described for patients with MC diagnosis.
- Area under the ROC curve of fecal calprotectin, ECP and EPX levels with clinical activity at each data collection time points among MC patients.
- Area under the ROC curve of fecal calprotectin ECP and EPX levels with histological activity at each data collection time points among MC patients

For definition of clinical and histological activity see section 8.3.1 and 8.3.2.

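### The histology rule collects four biopsies per segment but scores two, and its subtype criteria can give a confirmed MC patient two subtypes or none

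*Protocol*

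**What the plan says.** **Sampling.** Section 7.4.1: "Four biopsies will be collected from each colon segment: rectum, sigmoid, descending, transverse and ascending". That is 20 biopsies per patient. Sections 4 and 7.1 confine specimen collection and histology to patients whose colonoscopy is macroscopically normal.

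**Scoring.** Section 7.4.2: "For each segment the worst values of both biopsies are to be used for evaluation". The sentence before it says that the diagnosis of MC and of its subtypes "can only be established if the histological findings are present in at least one biopsy of at least two segments of the colon".

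**Criteria in 7.4.2, per segment.**
- MC, whatever the subtype: intraepithelial lymphocytes (IEL) above 5 per 100 cells, and/or collagen layer above 5 µm.
- Lymphocytic colitis (LC): IEL at least 20 and collagen below 10 µm.
- Collagenous colitis (CC): irregularly thickened collagen of at least 10 µm, with no condition on IEL.
- IC: collagen above 5 and below 10 µm, and/or IEL above 5 and below 20.

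**Background definition of IC.** Section 2.1 gives the same IC ranges but adds "without reaching the thickness or number required for the diagnosis of CC or LC". Section 7.4.2 has no such clause.

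**Where the rule is used.** The primary endpoint (8.1) is "Number of patients with confirmed diagnosis of MC (any subtype) over the total number of colonoscopies performed in all patients included in the study". The proportion with each subtype is a secondary endpoint (8.2). Section 8.3.2 defines histological remission differently for CC, LC and IC.

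**The concern.** There are two separate faults, and they reach different endpoints.

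1. **Number of biopsies read.** The word both presupposes two biopsies per segment, while four are taken. A worst-value rule becomes easier to satisfy as more biopsies are read, and the MC limits are low. The two readings can therefore classify the same patient differently, and this classification is the primary numerator.

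2. **Subtype assignment.** Without the exclusion clause, IC overlaps with LC and with CC. Because the two-segment rule also governs subtypes, and nothing says how to label a patient whose segments differ, some confirmed MC patients meet no subtype. The three subtype proportions can then sum to more or less than the MC proportion. A patient with two labels has two remission definitions, and a patient with no label has none.

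**Working it through.** **Step 1. The plan's own precision figure.** Section 9.2 gives N = 300, prevalence 10–15% and a margin below 4.5%. The half-width 1.96 × √(p(1−p)/300) is 3.39 points at 10% and 4.04 points at 15%. Expected MC patients at 10%: 0.10 × 300 = 30. Both statements reproduce, so the sample size is not at fault.

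**Step 2. Overlap within one segment.** The 7.4.2 limits give three collagen bands and three IEL bands. Subtypes met under the text of 7.4.2, taking collagen of 10 µm or more as irregularly thickened:

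| Collagen | IEL ≤ 5 | IEL > 5 to < 20 | IEL ≥ 20 |
|---|---|---|---|
| ≤ 5 µm | not MC | IC | LC |
| > 5 to < 10 µm | IC | IC | **LC and IC** |
| ≥ 10 µm | CC | **CC and IC** | CC |

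Two of the eight MC-positive cells carry two subtypes. With the section 2.1 exclusion added, each of the eight carries exactly one.

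**Step 3. Gap across segments.** Take a patient with IEL ≤ 5 throughout, collagen 12 µm in one segment, 7 µm in one other, and normal collagen elsewhere.
- MC: collagen above 5 µm in two segments, so confirmed.
- CC: one segment only, so not confirmed.
- IC: one segment only (the 7 µm one), so not confirmed.
- LC: no segment.

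The patient counts in the primary numerator and has no subtype. The IEL condition matters: if the 12 µm segment had IEL between 6 and 19, it would also meet IC under 7.4.2, and IC would be present in two segments.

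To see how general this is, take a patient with exactly two abnormal segments. Eight MC-positive patterns give 8 × 9 / 2 = 36 unordered pairs. Under the text of 7.4.2, 14 of 36 share no subtype. If the exclusion is restored segment by segment, 21 of 36 share none, because the double-labelled cells lose their IC label. These are counts of patterns, not of patients.

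**Step 4. Effect on remission (8.3.2).** Take a patient with LC and IC at diagnosis who has IEL 15, collagen 7 µm and Geboes below 3.1 at Month 24. As LC the patient is in remission (IEL not above 20). As IC the patient is not, since both IEL and collagen exceed 5. With about 30 MC patients, one patient is 1/30 = 3.3 points.

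**Step 5. Two versus four biopsies, illustration only.** Let q be the chance that one biopsy exceeds an MC limit, assumed equal and independent across a patient's biopsies. With b biopsies read, a segment is positive with probability s = 1 − (1−q)^b, and MC is confirmed with probability P(Binomial(5, s) ≥ 2).

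| q (assumed) | b = 2 | b = 4 |
|---|---|---|
| 0.01 | 0.4% | 1.4% |
| 0.02 | 1.4% | 5.1% |
| 0.05 | 7.8% | 23.3% |
| 0.10 | 24% | 56% |
| 0.30 | 82% | 99% |
| 0.50 | 98% | 100% |

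These are probabilities for a biopsied patient. To carry a difference to the primary endpoint, multiply it by the share of all colonoscopies belonging to biopsied patients with that q. The protocol gives neither that share nor q.

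Independence is also an assumption. If all biopsies from a patient agree, the two readings give the same answer. If instead a 2% average rate comes from one fifth of patients at q = 0.10 and the rest at zero, the difference is 0.20 × (56 − 24) = 6.4 points, against 5.1 − 1.4 = 3.7 under a uniform 2%.

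**The case against.** **The biopsy count may be leftover wording.** The sentence before the scoring rule accepts a finding in any one biopsy of a segment and sets no limit of two. Nothing says that two of the four are left unread. One central pathologist confirms every diagnosis, so sites would not diverge. This makes the worst of all four the more natural reading and lowers the practical risk. It does not remove the contradiction, since the scoring sentence is explicit and the Month 24 text in section 7.1 gives no count.

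**Section 2.1 shows the intended order.** LC already requires collagen below 10 µm, CC has no IEL limit, and 2.1 places IC last. The intended precedence can therefore be inferred. But 2.1 is background, it puts CC above 10 µm where 7.4.2 says at least 10 µm, and its clause does not close the two-segment gap.

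**The subtype faults do not touch the primary endpoint.** This stands. A reader might infer that overlapping subtypes make MC prevalence itself uncertain. They do not: MC has its own criterion, and the endpoint counts any subtype.

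**A large shift in prevalence cannot be shown.** This also stands. Applying assumed false-positive rates of 2% and 5% to all 90% of patients without MC gives shifts of 3.3 and 14.0 points, and a reader might set these against the 4.5-point margin. The documents do not support that. The rates are invented, 1% would give less than 1 point (0.90 × 1.05), and patients with abnormal colonoscopies count in the denominator but are not biopsied on this pathway.

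**Conclusion.** The rule is wrong as written in two respects and should be fixed.

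- **Primary endpoint.** Sections 7.4.1 and 7.4.2 disagree on the number of biopsies, and MC confirmation can depend on it. The size cannot be derived from the protocol. It also matters whether the two segments must show the same finding, for example raised collagen in one and raised IEL in another; the text does not say.
- **Subtypes and remission.** The overlap (two of eight abnormal combinations) and the two-segment gap follow from the text with no assumption beyond reading 7.4.2 literally. Subtype proportions need not sum to the MC proportion, and the remission definition can be ambiguous or absent. How many patients are affected is unknown.

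The pathologist applies this rule at reading, so an analysis plan cannot repair it afterwards if biopsies were left unread.

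**What to change.** 1. Reconcile 7.4.1 and 7.4.2 to one stated number of biopsies read per segment. If it is fewer than the number collected, say how they are chosen. Use the same number at baseline and at Month 24.
2. State whether the two segments must show the same finding, for MC and for each subtype.
3. Give each confirmed MC patient exactly one subtype by a patient-level hierarchy consistent with section 2.1: CC if its criterion is confirmed; otherwise LC if its criterion is confirmed; otherwise IC. Apply the exclusion to patients with confirmed CC or LC, not segment by segment, since that would widen the gap from 14 to 21 of 36 pairs. Under this hierarchy the 12 µm and 7 µm patient is labelled IC and takes the IC remission definition; the sponsor should confirm that this is intended.
4. Reconcile the CC limit between 2.1 and 7.4.2.

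The cost is a few lines in 2.1, 7.4.1 and 7.4.2 and a change to the pathologist's form. No extra biopsies are needed, although reading four rather than two adds reading time.
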